5.4 Recruitment Period

Part 1 of the trial is expected to begin Q1 2016.

Patients will be sequentially enrolled to dose-escalation cohorts until completion of Dose Level 4 or establishment of an MTD, whichever comes first, expected by Q1 2017.

Enrollment to Part 2 of the trial will commence upon establishment of the Q2W RP2D.

Enrollment is expected to complete by Q4 2019.

5.5 Number of Patients

In total, approximately 63-72 patients will be included in this trial.

It is estimated that approximately 12-15 patients will be enrolled to receive increasing doses of Sym015 during Part 1. The exact number of patients will depend upon the observed tolerability of Sym015 and the potential for adding additional patients to a cohort to assure a sufficient number of evaluable patients per cohort. For details, refer to Section [7.1.3.2](#).

It is estimated that approximately 51-57 patients will be enrolled to receive Sym015 at the RP2D on a Q2W schedule during Part 2. Three cohorts will be included:

- **Basket Cohort**: Approximately 25 patients with *KRAS* WT, advanced solid tumor malignancies with documented *MET*-amplification will be enrolled and treated. A subset of approximately 6 patients will have received prior therapy with a *MET*-targeting TKI.
Note: Effective with protocol version 8.0 (December 2018), accrual to the Basket Cohort is suspended.
NSCLC *MET*-Amplified patients entered to the Basket Cohort will be counted toward the NSCLC *MET*-Amplified Cohort; NSCLC *MET*^{Ex14Del} patients entered to the Basket Cohort will be counted toward the NSCLC *MET*^{Ex14Del} Cohort; patients with both will be counted as *MET*-Amplified.
- **NSCLC *MET*-Amplified Cohort**: approximately 20 patients with advanced NSCLC with documented *MET*-amplification will be enrolled and treated. Patients may have received prior therapy with *MET*-targeting agents and/or EGFR-targeting agents.
- **NSCLC *MET*^{Ex14Del} Cohort**: approximately 6-12 patients with advanced NSCLC with documented *MET*^{Ex14Del} will be enrolled and treated. Tumors need not be *MET*-amplified, and patients may have received prior therapy with *MET*-targeting and/or EGFR-targeting agents.

Note: NSCLC patients with tumors identified as both *MET*-Amplified and *MET*^{Ex14Del} will be enrolled to the *MET*-Amplified cohort.

For details regarding the sample size considerations, refer to Section [10.1](#).

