5.2 Discussion of Trial Design

5.2.1 Rationale for Trial Design

Part 1 of this trial utilizes a standard dose-cohort escalation with groups of a minimum of three patients evaluated for safety and tolerability of Sym015 in each cohort. In the event of a DLT, a cohort will be expanded to six patients. If tolerability is demonstrated (0/3 DLT, 1/6 DLT) in any cohort, escalation to the next dose level will be permitted. This part of the trial is designed to select a safe and well-tolerated dose of Sym015 on a Q2W schedule. Part 2 of this trial is

designed to evaluate the antitumor activity of Sym015 administered at the selected RP2D on a Q2W schedule.

The choice of a basket cohort (i.e., patients with *MET*-amplified, *KRAS* WT, advanced solid tumor malignancies of any tissue origin) for Part 2 is expected to allow for effective recruitment of patients with this relatively rare molecular alteration within a reasonable period of time. Emerging literature allowed for the identification of specific tumor types that are more likely to respond to Sym015 treatment (e.g., NSCLC).

Note: Effective with protocol version 8.0 (December 2018), accrual to the Basket Cohort is suspended.

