7.3 Blinding

Not applicable as this is an open-label trial.

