8.3 Disease Assessments

8.3.1 Disease Status Evaluation by CT or MRI

The anti-tumor activity of Sym015 will be assessed by the Investigator, or qualified designee, according to RECIST v1.1 (29). Refer to [Appendix 1](#).

Patients will undergo imaging by CT or MRI of neck, chest, abdomen and pelvis as indicated based on tumor type and clinical judgment in order to follow the underlying malignancy. The use of CT or MRI must be consistent per patient throughout the trial. Use of contrast is preferred but is at the discretion of the Investigator, as medically indicated.

- Screening

Note: A CT/MRI performed within 28 days prior to Day 1 may be used for evaluation of eligibility and as baseline scan, provided that the CT/MRI has been performed according to the protocol requirements

- EOC2 and end of every second cycle thereafter, i.e., EOC4, EOC6, EOC8, etc.

Note: May be performed at any time during the week prior to Day 1 of the next cycle, including Day 1 of the next cycle, prior to dosing (provided results are available prior to study drug administration)

- Suspected PD (as soon as possible)
- At least 28 days following an OR (PR, CR)
- EOT (if >3 weeks since previous CT/MRI)

- At 1M FUP (if PD was not documented before or at EOT)

If PD is documented at any time, no further disease assessments will be required. Patients with documented PD will be discontinued from Sym015 so that alternative management of their malignancy may be considered.

To be assigned a status of PR or CR, changes in disease status must be confirmed by repeat imaging studies performed no less than 28 days (4 weeks) after the criteria for response are first met. In the case of SD, follow-up measurements must have met the SD criteria at least once after trial entry at a minimal interval in general no less than 6-8 weeks from first dose of Sym015.

Imaging data (imaging studies and derived assessments) will be stored by the sites and will be available upon request for potential review by the Sponsor or an independent radiology reviewer. For Part 2 only: In addition, imaging studies will be sent to an imaging facility for storage in order to ensure central availability and readiness for read at a future time upon Sponsor or Health Authority request.

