10.4 Primary Endpoint and Analysis

10.4.1 Part 1, Dose-Escalation

The primary objective of the dose-escalation part is to assess the safety and tolerability of Sym015. This will be assessed by the primary endpoint for Part 1, occurrence of DLTs during Cycle 1 of Sym015 administration.

All DLT events will be listed by dose cohort and patient. A summary table of DLTs by System Organ Class (SOC) and Preferred Term will be presented for each dose cohort, if applicable. The summaries will include number of DLTs, and number and percentages of patients experiencing a DLT. The definition of a DLT is included in Section 9.5.1.

The MTD is defined as the highest dose with a maximum of 1 out of 6 patients experiencing a DLT. The MTD may or may not be found within the dose levels tested. Based on an overall evaluation of the dose-escalation part, the Q2W RP2D and highest safe dose tested will be selected. The Q2W RP2D might not necessarily be the MTD or the highest administered dose.

10.4.2 Part 2

The primary objective of Part 2 is to evaluate the antitumor activity of Sym015 when administered at the Q2W RP2D. The primary endpoint is documented, confirmed OR, defined as documented PR or CR and assessed by RECIST v1.1 at any time during trial participation by Investigator assessment. The assessment will be performed after completion of Part 2 of the trial.

Number and percentages of patients with documented OR will be presented including corresponding 90% exact Confidence Intervals (CI), separately for each cohort.

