21.7 Protocol Amendment 7 dated 07-Dec-2018

1. Effective with this protocol amendment, accrual to the Basket Cohort is suspended. Emerging literature allowed for the identification of specific tumor types that are more likely to respond to Sym015 treatment (e.g., NSCLC). With this change, a new cohort of NSCLC *MET*-amplified patients has been added to Part 2 of the trial design, for a total of three cohorts.
2. With the suspension of the Basket Cohort, NSCLC *MET*-amplified patients entered to the Basket Cohort will be counted toward the NSCLC *MET*-Amplified Cohort; NSCLC *MET*^{Ex14Del} patients entered to the Basket Cohort will be counted toward the NSCLC *MET*^{Ex14Del} Cohort; patients with both will be counted as *MET*-Amplified.
3. Updated clinical experience information have been added to the scientific background.
4. According to the ASCO/CAP guidelines for testing of HER2 amplification, *MET*-amplification may be defined as positive with a MET/CEP7 ratio of >2.2 (occasionally 2.0). Symphogen has opted to change the cutoff to ≥ 3.0 based on emerging data that suggest higher degrees of *MET*-amplification are associated with higher degree of response.
5. Specified that concomitant therapy with bisphosphonates and denosumab are allowed during the dosing portion of the trial.
6. Clarified that after the Screening assessments, targeted physical examination may be performed as indicated.
7. The number of pharmacokinetic timepoints have been reduced for patients entered to the NSCLC cohorts.
8. The mandatory post-dosing tumor biopsy scheduled to be performed at the EOC2 or upon disease progression is now optional.
9. Clarified that all analyses will be related to and used only in connection with the data collected in the present trial as well as future development of Sym015.
10. Clarified that EOC assessments may be performed at any time during the week prior to Day 1 of the next cycle, including Day 1 of the next cycle, prior to dosing.
11. Clarified that initial SAE and follow-up SAE information are to be submitted within 24 hours of awareness.
12. Due to the new cohort sample sizes, an initially planned interim analysis becomes obsolete and will no longer be performed.
13. Guidelines pertaining to the General Data Protection Regulation have been added.
14. Formatting adjustments, typographical corrections, outline modifications, and wording/abbreviation changes are included.

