3.2.4.1 Protocol Sym015-01	
As of Amendment 6, a total of 7 MET-amplified patients have been enrolled in the ongoing Part 2 Basket Cohort of this trial to receive Sym015 at a loading dose of 18 mg/kg delivered over 1.5 hours, followed by Q2W maintenance doses of 12 mg/kg delivered over 1 hour... Other study drug-related AEs have been limited to fatigue (Grade 2) and prolonged prothrombin time (Grade 1). Accrual to this portion of the trial continues.
	
As of September 2018, a total of 21 MET-amplified patients and 2 MET^{Ex14Del} patients have been enrolled in the ongoing Part 2 portion of this trial to receive Sym015 at a loading dose of 18 mg/kg delivered over 1.5 hours, followed by Q2W maintenance doses of 12 mg/kg delivered over 1 hour... In another patient, the SAEs of Grade 3 anasarca and Grade 3 hypoalbuminemia (both possibly related) have been reported. Other study drug-related AEs have been limited to Grade 2 fatigue and mouth sores, and Grade 1 asthenia, anorexia, gastric pain, abdominal cramping, abdominal gas, nausea, diarrhea, constipation, xerosis, pruritus, and voice change... Accrual to the Part 2 portion of the trial continues.
 
Note: Effective with protocol version 8.0 (December 2018), accrual to the Part 2 Basket Cohort comprised of patients with MET-amplified solid tumor malignancies is suspended; accrual will continue to cohorts of patients with MET-amplified NSCLC or MET^{Ex14Del} NSCLC.

Table 22 Protocol Amendment 7

SECTION	ORIGINAL TEXT	NEW TEXT

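### The NSCLC MET-Amplified response rate pools newly enrolled patients with Basket patients whose first scans were already due when the cohort was created, with no separate estimate

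*Protocol*

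**What the plan says.** Protocol section 5.5 plans about 20 patients for the NSCLC MET-Amplified Cohort. It adds that NSCLC MET-amplified "patients entered to the Basket Cohort will be counted toward the NSCLC" MET-Amplified Cohort. It has a matching rule for exon 14 patients, and "patients with both will be counted as *MET*-Amplified".

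Section 21.7 dates Amendment 7 to 7 December 2018. That amendment suspends Basket accrual and adds the NSCLC MET-Amplified Cohort as new. The new text of section 3.2.4.1, given in the amendment table, reports enrolment so far: "As of September 2018, a total of 21" MET-amplified patients, and 2 with the exon 14 alteration, had entered Part 2. The number with NSCLC is not stated.

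Section 5.2.1 gives the reason for the NSCLC focus: "Emerging literature allowed for the identification of specific tumor types that are more likely to respond to Sym015 treatment", with NSCLC as the example.

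On masking, section 7.3 says "Not applicable as this is an open-label trial". Section 8.3.1 schedules response imaging at "EOC2 and end of every second cycle thereafter", with confirmation of a response at least 28 days later. Section 10.4.2 reports confirmed, investigator-assessed response with a 90% exact interval, "separately for each cohort". It does not separate patients carried over from the Basket Cohort from those enrolled afterwards.

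**The concern.** Carrying patients into a cohort is harmless if the cohort was defined without regard to how they had responded. Here the histology was singled out, and the cohort formed, at a time when investigators and sponsor could see at least the first scans of patients who would then count in it. If those scans played any part in the decision, the same responses would both motivate the cohort and serve as its evidence. Carrying over every patient of the chosen histology, non-responders included, does not remove this, because the choice of histology would itself depend on outcome.

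At stake is the primary Part 2 estimate for this cohort. The exact interval treats all 20 patients as a sample whose inclusion is unrelated to outcome, and it makes no allowance for selection. With one pooled figure, a reader of the results could not tell how much of the rate rests on patients enrolled after the cohort was defined.

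**Working it through.** **1. The plan's own intervals.** Table 10 lists 90% exact limits for N=20 and N=25. The Clopper-Pearson limits are the 5% quantile of Beta(x, n−x+1) and the 95% quantile of Beta(x+1, n−x). All 32 rows reproduce (largest difference 5×10⁻⁸). For example, 4/20 gives 7.1% to 40.1%. The intervals are computed correctly; the question is which patients enter them.

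**2. What could be seen by 7 December 2018.** I take enrolment as Cycle 1 Day 1, two 28-day cycles to the first scan (56 days), and 28 more days to confirmation.

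- Start on 30 September 2018: first scan due 30 Sep + 56 days = 25 November 2018; earliest confirmation 28 days later, 23 December.
- Latest start with a first scan due by 7 December: 7 Dec − 56 days = 12 October.
- Latest start for a confirmed response by 7 December: 7 Dec − 84 days = 14 September.

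So first scans were already due for every patient enrolled by the end of September and still on trial. The confirmed endpoint could be known only for those who started by about 14 September.

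**3. Possible size of the bias.** Let k of 20 patients be carried over, let p be the true response rate, and suppose the cohort was opened only if at least r of those k responded. Neither k nor r is in the protocol; both are assumptions. The expected pooled rate is

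(E[X | X ≥ r] + (20 − k)p) / 20, with X ~ Binomial(k, p).

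Example with p = 0.20, k = 5, r = 2:

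- P(X=1) = 5 × 0.2 × 0.8⁴ = 0.4096
- P(X≥2) = 1 − 0.3277 − 0.4096 = 0.2627
- E[X | X≥2] = (1 − 0.4096)/0.2627 = 2.247
- Pooled: (2.247 + 15 × 0.2)/20 = 26.2%

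Expected pooled rate when the true rate is 20%, with the probability of meeting the trigger in brackets:

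| | k=3 | k=5 | k=8 | k=10 |
|---|---|---|---|---|
| r=1 | 23.1% (0.49) | 22.4% (0.67) | 21.6% (0.83) | 21.2% (0.89) |
| r=2 | 27.4% (0.10) | 26.2% (0.26) | 24.7% (0.50) | 23.9% (0.62) |
| r=3 | 32.0% (0.01) | 30.6% (0.06) | 28.7% (0.20) | 27.5% (0.32) |

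The excess is 1.2 to 12.0 points. The top value needs three responders among three, which has probability 0.2³ = 0.8% at a true 20%. Over the same grid the excess is 0.2 to 9.7 points at a true 35% and 0.0 to 7.5 points at a true 50%. With no outcome-dependent trigger it is zero.

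**4. Effect on the interval.** At a true 20% with N=20 and no selection, coverage is 95.6% and the lower limit exceeds the truth with probability 3.2%. With k=5 and r=2 these become 91.1% and 8.9%. Coverage is still above the nominal 90%, but the error on the optimistic side passes its nominal 5%. Across the twelve cells above, coverage falls below 90% in four (k=3 with r=2 or 3; k=5 or 8 with r=3), with a minimum of 75.8%.

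**The case against.** The strongest reply is that no selection on outcome is shown. The rule works by histology and MET status and carries over every such patient. A reader might infer that responders were picked and moved; section 5.5 does not support that. The stated reason for the NSCLC focus is outside literature, and section 3.1.3 cites response data for other MET inhibitors in NSCLC. This stands in full: the most that can be said is that an outcome-informed definition cannot be excluded.

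A reader might also infer that both NSCLC cohorts are new and equally affected. The documents do not support this either. Amendment 6 (20 November 2017) had already added a separate cohort of 6-12 NSCLC patients with the exon 14 alteration. Section 8.3.3 speaks of its establishment at version 8.0, but Amendment 7 calls only the MET-Amplified cohort new. Basket entry required MET-amplification, and patients with both alterations count as MET-Amplified, so few or no Basket patients should reach the exon 14 cohort.

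Third, the Part 2 analysis is descriptive: no hypothesis test, no type I error or power basis, and no decision threshold. This limits the consequence. It does not remove it, because the response rate is the primary endpoint and its interval is the inference offered.

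Fourth, section 10.1 leaves analysis details to the SAP, which was not available for this review. If the SAP already splits the cohort by protocol version, the point is met. The carry-over rule and the per-cohort rate are, however, fixed in the protocol itself.

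Finally, the two groups differ in more than timing. Basket patients qualified at an amplification ratio above 2.2, had to be KRAS wild-type, and were mostly to be free of prior MET-targeting therapy. The NSCLC MET-Amplified criteria require a ratio of at least 3.0, set no KRAS condition and allow prior MET-targeting agents. A difference between the two rates therefore could not be put down to timing alone. This is a caution on interpretation, not a reason to withhold the split.

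**Conclusion.** The point holds for the NSCLC MET-Amplified Cohort, as a gap in transparency rather than a demonstrated bias. The dates show that first scans of patients enrolled by September 2018 were due before the cohort was created, although confirmed response could be known only for those who started by about 14 September. The protocol pools these patients with later ones, does not say how many there are, and does not say whether their responses had been reviewed.

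The range of about 1 to 12 points at a true 20% rests wholly on the assumed 3-10 carried over and the assumed trigger of 1-3 responses. It shows what an outcome-informed choice could do and is not an estimate of what happened. For the exon 14 cohort no magnitude is claimed.

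**What to change.** In section 10.4.2, for the NSCLC MET-Amplified Cohort:

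- Report the response rate and 90% exact interval for patients first dosed under protocol version 8.0 beside the pooled rate. The former is free of any selection informed by Basket outcomes.
- State the number carried over from the Basket Cohort.
- State whether Basket responses were reviewed before Amendment 7.
- Note that the two groups also differ in amplification cutoff, KRAS and prior-therapy criteria, so that a difference in rates is not read as an effect of timing alone.

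For the exon 14 cohort it is enough to list any patients carried over from the Basket Cohort.

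The cost is one extra table row and two short statements, with no new patients or data. The restricted estimate is less precise: with 5 of 20 carried over (an assumption), 3/15 gives 5.7% to 44.0%, against 7.1% to 40.1% for 4/20.

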5.6 End of Trial

The end of trial will be reached at the latest 1 month (30 +7 days) after the last patient has been withdrawn from Sym015.

6. PATIENT SELECTION AND WITHDRAWAL

Questions regarding patient eligibility must be addressed and resolved by the Investigator in consultation with the Sponsor or designee prior to enrollment.

6.1 Inclusion Criteria

For inclusion in the trial, all of the following criteria must be fulfilled:

1. Written informed consent given before any trial-specific procedure is initiated
2. Male or female, at least 18 years of age at the time of informed consent
3. Eastern Cooperative Oncology Group (ECOG) performance status (PS) of 0 or 1
4. Life expectancy >3 months assessed during Screening
5. Documented (histologically- or cytologically-proven) solid tumor malignancy that is locally advanced or metastatic, and that is refractory to standard therapy or for which no standard therapy is available or accessible (i.e., patients must have recurrent and/or progressive disease and be without available therapeutic options)
6. Part 1 ONLY: Tumor documented to be *KRAS* WT by local assessment according to institutional standards. If *KRAS* WT is not previously documented and if archival tissue is not available for pretrial assessment, patient must be willing to undergo a tumor biopsy to confirm eligibility
7. Part 2 ONLY:
 - a. Measurable disease according to the RECIST v1.1 that has been confirmed by computed tomography (CT) or magnetic resonance imaging (MRI) within 4 weeks prior to C1/D1

Note: Measurable disease is defined as 1 or more target lesions assessed by CT or MRI. A tumor lesion situated in a previously irradiated area is considered measurable only if subsequent PD has been documented in the lesion

- b. Basket Cohort ONLY:
 - Tumor documented to be *KRAS* WT by local assessment according to institutional standards. If *KRAS* WT is not previously documented and if archival tissue is not available for pretrial assessment, patient must be willing to undergo a tumor biopsy to confirm eligibility.

Note: Peripheral blood collection for *KRAS*-mutation assessment in ctDNA will be allowed as a local pre-screening methodology by Guardant360* analysis. Other liquid biopsy methodologies, if used to detect *MET*^{Ex14Del}, are acceptable alternatives.

*<<http://guardanhealth.com>>

- Confirmed *MET*-amplification by local assessment; i.e., *MET* gene copy number to control probe ratio [G:CN] >2.2 scored in 50 tumor nuclei by FISH, chromogenic *in situ* hybridization (CISH), silver *in situ* hybridization (SISH) or

similar (5), or a copy number ≥ 5 by next-generation sequencing (NGS) or quantitative polymerase chain reaction (qPCR)

Note: Peripheral blood collection for MET-amplification assessment in ctDNA will be allowed as a local pre-screening methodology provided results are 3+ by Guardant360* analysis (or equivalent to 3+ by Guardant360 if an alternative Sponsor-approved methodology is used), and provided subsequent required confirmatory tumor tissue evaluation results meet the above inclusion criterion.

*<http://guardanhealth.com>

- No prior therapy with MET-targeting agents

Note: An exception will be a subset of approximately 6 patients entered to the Basket Cohort after having received prior therapy with a MET-targeting TKI.

- Willingness to undergo a pre- and post-dosing biopsy (maximum of 2 biopsies) from primary or metastatic tumor site(s) considered safely accessible for biopsy

c. NSCLC MET-Amplified Cohort ONLY:

- Documented NSCLC meeting disease criteria as defined above
- Documented *MET*-amplification by either:
 - Local assessment in a recent* tumor biopsy; i.e., G:CN ≥ 3.0 scored in 50 tumor nuclei by FISH, CISH, SISH or similar assay, or a copy number ≥ 5 by NGS or qPCR (subsequent central confirmation required, however patient may be enrolled and treated based on local assessment, before central confirmation results have been obtained)

*Tissue for local assessment may be from a recent tumor biopsy, defined as one performed since last documented disease progression as part of the site's usual practice, and where no intervening antineoplastic therapy has been administered; otherwise tissue from a newly performed biopsy must be obtained and submitted.

- Central confirmation** in a newly performed pre-dosing tumor biopsy; i.e., G:CN ≥ 3.0 scored in 50 tumor nuclei by FISH

**If central confirmation of *MET*-amplification status cannot be assessed in tumor due to assay failure/technical error, the Sponsor may decide to enroll based on *MET*-amplification detected by Guardant360 on a case per case basis (see Note below regarding Guardant360 analysis).

- May have received prior therapy with MET-targeting and/or EGFR-targeting agents (antibodies or TKIs)
- Willingness to undergo a pre-dosing biopsy (mandatory unless a recent* tumor biopsy as defined above is available), and potentially a biopsy at the End of Cycle 2 (EOC2) (optional), from a primary or metastatic tumor site considered safely accessible for biopsy

Note: Peripheral blood for ctDNA analysis by Guardant 360 will be obtained for assessment of *MET*-amplification status. As data are acquired on concordance between findings in tumor tissue versus ctDNA, the Sponsor may decide to transition to screening for *MET*-amplification using Guardant360 analysis only (e.g., 2+ or 3+ amplification score) without requiring confirmation in a recent or newly performed tumor biopsy.

d. NSCLC *MET*^{Ex14Del} Cohort ONLY:

- Documented NSCLC meeting disease criteria as defined above
- Documented *MET*^{Ex14Del} (tumors need not be *MET*-amplified)

Note: *MET*^{Ex14Del} status to be documented according to local institutional standards. Assessment in ctDNA by Guardant360 technology or equivalent is allowed. Tissue from a recent* or newly performed pre-dosing tumor biopsy must be submitted for central assessment.

*Recent tumor biopsy, defined as one performed since last documented disease progression as part of the site's usual practice, and where no intervening antineoplastic therapy has been administered; otherwise tissue from a newly performed biopsy must be obtained and submitted.

- May have received prior therapy with *MET*-targeting and/or EGFR-targeting agents (antibodies or TKIs)
- Willingness to undergo a pre-dosing biopsy (mandatory unless a recent* tumor biopsy as defined above is available), and potentially a biopsy at the EOC2 (optional), from a primary or metastatic tumor site considered safely accessible for biopsy

Note: Peripheral blood for ctDNA analysis by Guardant 360 will be obtained for assessment of *MET*^{EX14Del} status.

8. If female and of childbearing potential, a negative pregnancy test
9. Male or female, either not of childbearing potential or agreeing to use a medically effective method of contraception as per institutional standards during the trial and for 4 months after the last dose of trial drug

